consent for research purposes under the Revised Common Rule. We provide justifications for the request in section 6.2.

Recruitment will proceed in 3 waves at each site, with caregivers in each wave randomly assigned either to a Tele-Savvy program or an attention control program called Caregiving During Crisis. The recruitment goal at each site in each wave is to enroll 10 caregivers for a Tele-Savvy program cohort and 6-7 caregivers to receive the Caregiving During Crisis self-guided program.

The study biostatistician will be responsible for generating randomization strings for each study site during each wave of recruitment, and for making the randomization strings available electronically in a secure location for access by the study coordinator.

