5.2 Handling of Study Interventions

Trained Tele-Savvy facilitators are used to lead all synchronous sessions, and an intervention manual is provided for both the facilitator and the caregivers participating in each program. Facilitators must complete a training program, and the facilitators for this pilot study at both sites program will have successfully completed the training before they begin leading the first program in this study. Facilitators also complete a checklist of objectives covered in each program session to help monitor treatment fidelity.

The Tele-Savvy program will be offered on a secure Emory University School of Nursing Canvas platform. The security of this platform has been demonstrated in a multi-site efficacy clinical trial, so there is little likelihood of its being penetrated in a way that might release individual's private information. Results and publications that come from the evaluation of this project will not identify caregivers by name or other PHI identifiers.

Caregivers assigned to the attention control condition, Caregiving During Crisis, will receive online instruction on how to use the self-guided intervention. This self-guided, online, asynchronous program will be accessible on the secure Emory University School of Nursing Canvas. Individual caregivers will access this program as often as they wish, using a secure password. Results and publications that come from the evaluation of this project will not identify caregivers by name or other PHI identifiers.

Because this is a pragmatic clinical trial, no members of the study team will be masked.

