The administrative study coordinator will electronically access the appropriate study site's randomization string (strings will be generated by the study biostatistician, see Section 4.3) after a caregiver returns completed baseline assessment forms. Randomization results will reveal whether the caregiver is assigned to the Tele-Savvy program or to the attention control group. Randomization will be performed within business 3 days of receipt of completed baseline assessment forms. The administrative study coordinator will then notify the Tele-Savvy facilitator at each study site of the randomization result, and the facilitator will notify caregivers about the treatment group to which they are assigned. The statistician will provide the randomization scheme (random sorting using 10% maximum allowable deviation using PASS 2020 software⁵⁶), which will be applied after the baseline assessment. For the Tele-Savvy intervention, because 10 caregivers at each site must be assembled in order to convene a cohort, a window of up to 3 weeks will be allowed between randomization of a caregiver to that treatment group and initiation of the intervention. For the attention control group, caregivers will be permitted to access the Caregiving During Crisis program anytime beginning 3 days after randomization.

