10.2 Data Management

All quantitative data from self-administered caregiver questionnaires will be stored in a REDCap database at the UConn Health site, and in a TONIC database at the Emory Healthcare site. Data from individual caregivers will be de-identified and stored using ID numbers. Each site will be responsible for maintaining in a password-protected file and server the document linking subject names and de-identified ID numbers. The clinical data manager at the UConn Health site ([name]) and co-investigator [name] at the Emory Healthcare site will be responsible for the protection of their respective site’s data files. Transfer of de-identified study data files to the study Biostatistician at Emory School of Nursing ([name]) will occur using secure file transfer software at each of the study sites. [name] will be responsible for conducting all quantitative data analyses.

Additionally, consistent with Objective 3 of this pragmatic clinical trial, we intend to implement procedures at both study sites whereby caregiver questionnaire results will be uploaded into electronic health record (EHR) systems. This is an innovative data management feature that has

the goal of enabling routine collection of these caregiver measures and inclusion of these measures into the EHRs at both health care systems. The clinical data manager at the UConn Health site ([name]) and co-investigator [name] at the Emory Healthcare site will be responsible for leading efforts to work with information technology staff at their sites to enable transfer of caregiver outcome measures to their respective EHR systems in such a way that these data are linked to the electronic records of the patients with ADRD who receive care by clinicians at these study sites.

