10.3.3 Metrics

[name] at the UConn Health site and [name] at the Emory Healthcare site will be responsible for monitoring the quality and completeness of self-administered questionnaires sent by study caregivers at each time point. Errors encountered will be forwarded to the study coordinator who will contact caregivers to resolve any data-related concerns regarding outcome measures. The study coordinator also will be available to answer questions from caregivers about the self-administered questionnaire items.

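### The person who randomizes caregivers can read the current site-and-wave list, and no order of assignment is fixed, so upcoming assignments are not concealed

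*Combined protocol and SAP*

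**What the plan says.** Section 4.3 gives the biostatistician two tasks. The first is "generating randomization strings for each study site during each wave of recruitment". The second, which concerns who can reach the list, is "making the randomization strings available electronically in a secure location for access by the study coordinator". The recruitment goal there is 10 Tele-Savvy and 6-7 control caregivers per site and wave, so each string covers about 16-17 assignments.

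Section 6.2.2 describes its use: "The administrative study coordinator will electronically access the appropriate study site's randomization string", and this happens "after a caregiver returns completed baseline assessment forms". On timing it says: "Randomization will be performed within business 3 days of receipt of completed baseline assessment forms". The coordinator then passes the result to the facilitator. Section 4.3 speaks of the study coordinator and Section 6.2.2 of the administrative study coordinator. Because 6.2.2 refers back to 4.3 for the strings, I read these as one role.

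Section 5.2 states: "Because this is a pragmatic clinical trial, no members of the study team will be masked".

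The document mentions no one-at-a-time release, no irrevocable registration before the string is consulted, no allocation log, and no rule that caregivers are randomized in the order their forms arrive.

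**The concern.** Opening the string only after baseline forms are back protects the baseline scores. It also hides the assignment of the first caregiver in a wave. It does not hide the second or any later assignment, because the coordinator has by then opened a list that covers the whole wave at that site. The secure location keeps other people out, but it does not limit what the coordinator can see.

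Knowing the next entries matters only if something can be done with them. Here something can: each caregiver may wait up to 3 business days, and the order among those waiting is not fixed. If two are waiting and the next two entries differ, the coordinator could decide who receives which program. Even well-meant choices, such as placing the more available or motivated caregiver in the live group program, would make the arms differ in prognosis.

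The primary outcome is a 4-item self-report of mastery, and the protocol tests an effectiveness hypothesis on it. A mixed model does not remove imbalance on motivation that nobody measured.

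**Working it through.** **The plan's own figure.** This point disputes no number. For completeness, the stated 80% power for 60 + 40 caregivers (Section 9.5) reproduces with a noncentral F and λ = f² × N, N = 100, df 1 and 98: f = 0.285 gives 0.806 and f = 0.282 gives 0.797.

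**Step 1: how much is visible.** With the string readable, all 16 of 16 (or 17 of 17) assignments in a wave are known once it has been opened. Suppose instead that entries were revealed singly, with totals fixed at 10:6 or 10:7. The best guess from past assignments would then be right for about 10.9 of 16 (68%) or 11.1 of 17 (65%). Always guessing Tele-Savvy is right for 10/16 = 63% or 10/17 = 59%.

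**Step 2: how often two caregivers wait together.** Section 6.2.2 allows up to 3 weeks (15 business days) between randomization to Tele-Savvy and program start, so a cohort's Tele-Savvy members are randomized within about that span. Assume the wave's 16-17 caregivers arrive evenly over it:

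- arrivals per day: 16/15 = 1.07 to 17/15 = 1.13
- arrivals per 3-business-day window: 3.2 to 3.4

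If the number waiting is Poisson, the chance of two or more is 1 − e^(−m)(1 + m). This is 83-85% for m = 3.2-3.4. With slower accrual, m = 1, it is 26%.

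**Step 3: how often the next entries include both arms.** For the next two entries:

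- 10:6 wave: 1 − [C(10,2) + C(6,2)] / C(16,2) = 1 − (45 + 15)/120 = 50%
- 10:7 wave: 1 − (45 + 21)/136 = 51%

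For the next three entries it is 75-77%. So on the protocol's own wave size and windows, a real choice would often be available.

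**Step 4: what steering would do (illustration; all inputs assumed).** Take 50 consecutive pairs among 100 caregivers, with a standard normal prognosis score.

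- Share of discordant pairs at 3:2: 2 × 0.6 × 0.4 = 0.48, so 24 pairs.
- Let s be the fraction of discordant pairs in which chance is overridden in favor of giving Tele-Savvy to the better-prognosis caregiver. The rest stay at 50:50, so that caregiver goes to Tele-Savvy in s + (1 − s)/2 of discordant pairs: 62.5% at s = 0.25 and 75% at s = 0.50.
- In a steered pair the better caregiver is on average 1/√π = 0.564 SD above the mean and the other 0.564 SD below.
- Difference between arms: 24 × s × 0.564 × (1/60 + 1/40) = 0.564 × s.
- Bias = 0.5 × difference, taking a correlation of 0.5 between prognosis and the analysed outcome.
- Standard error = √(1/60 + 1/40) = 0.204, and z = bias / 0.204.
- Two-sided type I error = Φ(−1.96 + z) + Φ(−1.96 − z).

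| s | Pairs overlapping | Difference in prognosis (SD) | Bias (SD) | z | Type I error |
|---|---|---|---|---|---|
| 0.25 | all | 0.14 | 0.07 | 0.35 | 6.4% |
| 0.50 | all | 0.28 | 0.14 | 0.69 | 10.6% |
| 0.25 | half | 0.07 | 0.035 | 0.17 | 5.3% |
| 0.50 | half | 0.14 | 0.07 | 0.35 | 6.4% |

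The formula treats the result as one unadjusted comparison of means. The planned hypothesis concerns change from baseline to 3 months in a mixed model (Sections 9.1 and 9.5), so the relevant correlation is the one between prognosis and change. The documents give no value for it.

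**The case against.** The strongest reply is that the text leaves a detail unstated and shows no fault. It does not describe what the coordinator sees on screen, the trigger is the caregiver's own return of forms, and the wait is capped at 3 business days. Steering also requires knowing who is promising, and the coordinator has an administrative role. Much of this stands: misuse is not shown, and the discretion is limited. But Section 4.3 makes the strings themselves available, and following Sections 4.3 and 6.2.2 as written leaves later entries open to the person who assigns.

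A reader might infer more than the documents support:

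- **That the coordinator could choose whom to invite.** Section 4.3 gives invitations to clinic staff or the health record system, after clinician confirmation. Enrollment and baseline assessment precede randomization. Only reordering or delay among enrolled caregivers remains.
- **That the coordinator decides when a baseline form counts as complete.** Section 10.3.3 gives monitoring of quality and completeness to other named site personnel. It then says: "Errors encountered will be forwarded to the study coordinator who will contact caregivers to resolve any data-related concerns regarding outcome measures". It does not link that contact to randomization timing.
- **That all 100 assignments are exposed.** Strings are made by site and wave, so it is about 16-17 at a time.
- **That absence of masking is itself the fault.** Masking and concealment are separate. An open pragmatic trial can still conceal the next assignment.

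It can also be said that a pilot whose stated primary goal is enrollment need not meet this standard. Yet the protocol tests a between-arm hypothesis on mastery, and protecting that comparison costs little.

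**Conclusion.** The point holds as a gap in allocation concealment within each site and wave. The unmasked person who assigns can read the remaining entries once the string is open, and neither order of receipt nor registration before release is required. Overlap of waiting caregivers is plausible: about 3 per window under even arrival over 15 business days, with both arms among the next two entries about half the time. If accrual is slower, the opportunity shrinks.

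The size of any bias is unknown. The figures of 0.07-0.14 SD and about 6-11% type I error rest on three assumptions: chance is overridden in 25-50% of discordant pairs, every consecutive pair is pending together, and prognosis correlates 0.5 with the analysed outcome. If half the pairs overlap, type I error is about 5-6%. If prognosis correlates weakly with change from baseline, the effect is smaller still. The case for changing the procedure rests on the opening it leaves and the low cost of closing it, not on these figures.

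**What to change.** In Sections 4.3 and 6.2.2, replace coordinator access to the string with single release, in one of two ways:

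- The biostatistician, or another person outside enrollment, holds the list and releases the next assignment on request.
- A randomization module that shows only the current caregiver's arm is used for both sites. Section 10.2 has data "stored in a REDCap database at the UConn Health site", but Emory uses TONIC, so REDCap cannot be assumed to be in place at Emory.

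In either case, state that an assignment is released only after the caregiver is irrevocably registered and the baseline form is locked, in time-stamp order of receipt of completed forms, and that each release is logged. If single release is already intended, writing it into these two sections is enough.

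The cost is one set-up step, a sentence or so in each section, and possibly a short wait for release. No extra staff are needed, and sample size and power do not change. One limit remains: if wave totals are fixed, about the last 2 assignments in a wave can still be deduced from earlier ones.

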5 STUDY INTERVENTIONS

5.1 Interventions, Administration, and Duration

The Tele-Savvy program, *a low-risk, psychoeducational, group-based intervention*, is grounded in social learning and stress process theory and its main goal is to produce improved caregiver mastery over the symptom management skills commonly encountered when supervising and caring at home for an older adult living with ADRD. Over the 7-week program, there are synchronous and asynchronous activities each week. The synchronous portion includes weekly scheduled videoconferences (60-80 min) that serve as an online classroom in which facilitators lead lectures and discussions and provide a venue for caregivers' interactions and sharing of their experiences. The majority of Tele-Savvy is asynchronous. Daily, caregivers access online 6- to 15-min prerecorded videos, each focused on one main learning objective. The lessons' didactic messages are delivered through expert presentations that are usually augmented by vignettes enacted by amateur actors playing a "caregiving family" in various dementia-stage-specific caregiving situations and using caregiving strategies in familiar settings. Caregivers can watch the lessons whenever and as often as they wish. The Canvas platform at Emory University houses the Tele-Savvy software that includes analytics to monitor caregivers' use of asynchronous material each week. Topics of the synchronous sessions progress from cognitive losses through caregivers' emotions, guiding behavior and decision-making skills, and family systems. Videos depicting caregiving situations follow a similar course as the more didactic videoconference topic presentations each week, ending with increasing caregiver mastery and the concept of caregiver village.

The attention control group will receive the self-guided Caregiving During Crisis program. Caregiving During Crisis is a fully online, asynchronous, professionally designed continuing education course aimed at developing the competency of informal caregivers of community-dwelling persons living with dementia to ensure the safety of that person and themselves during this time of the COVID-19 pandemic. The course, readily accessible by home computer or smartphone, describes methods of home infection control and prevention to create a Safe Home space, strategies for safely leaving and re-entering the home (e.g., to shop), additional strategies for safely allowing service personnel (e.g., home health aides or electricians) and select family members to enter the Safe Home space, and risk management strategies to frame decisions when/if COVID restrictions are relaxed or revoked.

5.2 Handling of Study Interventions

Trained Tele-Savvy facilitators are used to lead all synchronous sessions, and an intervention manual is provided for both the facilitator and the caregivers participating in each program. Facilitators must complete a training program, and the facilitators for this pilot study at both sites program will have successfully completed the training before they begin leading the first program in this study. Facilitators also complete a checklist of objectives covered in each program session to help monitor treatment fidelity.

The Tele-Savvy program will be offered on a secure Emory University School of Nursing Canvas platform. The security of this platform has been demonstrated in a multi-site efficacy clinical trial, so there is little likelihood of its being penetrated in a way that might release individual's private information. Results and publications that come from the evaluation of this project will not identify caregivers by name or other PHI identifiers.

Caregivers assigned to the attention control condition, Caregiving During Crisis, will receive online instruction on how to use the self-guided intervention. This self-guided, online, asynchronous program will be accessible on the secure Emory University School of Nursing Canvas. Individual caregivers will access this program as often as they wish, using a secure password. Results and publications that come from the evaluation of this project will not identify caregivers by name or other PHI identifiers.

Because this is a pragmatic clinical trial, no members of the study team will be masked.

5.3 Concomitant Interventions

Not applicable to this study.

5.4 Adherence Assessment

Tele-Savvy facilitators will be responsible for documenting attendance by caregivers at each synchronous session, which will be reviewed to determine caregiver adherence to the synchronous component of the intervention. The secure Tele-Savvy online platform located at Emory University will record each time a caregiver accesses educational and skill-building material for the asynchronous component of the intervention. Caregivers will be issued user identification numbers and passwords for both security purposes, and so that their adherence to the asynchronous material can be documented and retrieved by approved study staff to determine their adherence. Attendance in 4 or more of the 7 synchronous sessions will be operationally defined as adherent, and adherence to asynchronous components will be measured as high-medium-low tertiles.

6 STUDY PROCEDURES

6.1 Schedule of Evaluations

Assessment	Baseline, Enrollment, Randomization:	3 months post- randomization (+ 2 weeks)	6 months post- randomization (+ 2 weeks)
Inclusion/Exclusion Criteria	X		
Enrollment/Randomization	X		
Demographics	X		
Caregiver mastery	X	X	X
Reactions to behavioral and psychological symptoms	X	X	X
Caregiver stress	X	X	X
Adverse Events	X	X	X

6.2 Description of Evaluations

Descriptions for the Schedule of Evaluations define what is to be done at each study period and include special considerations or instructions for evaluations.

This section should include definitions of the row headings in the Schedule of Evaluations and any special instructions. All of the items listed on the Schedule of Evaluations should be described in this section.

6.2.1 Screening Evaluation

Opt-in/Opt-out Procedure

Participation in the programs (Tele-Savvy or the control program) is completely voluntary. Caregivers will be provided information and will have the opportunity to opt-in or opt-out. Because of this, and the intention of this study to examine whether it can be effectively be rolled out in a real-world health care setting, we request a waiver of informed consent for research purposes under the Revised Common Rule and provide the following justifications:

(i) The research involves no more than minimal risk to the subjects:

The research presents no more than minimal risk of harm or discomfort to subjects beyond those ordinarily encountered in daily life or during routine clinical exams or tests. Participation in the programs (Tele-Savvy or the control program) is completely voluntary. Caregivers will be provided information and will have the opportunity to opt-in or opt-out.

Tele-Savvy is a low risk *psychoeducational, group-based program*, grounded in social learning and stress process theory and its main goal is to produce improved caregiver mastery over the symptom management skills commonly encountered when supervising and caring at home for an older adult living with ADRD. Offering the Tele-Savvy program as proposed in this pilot study is similar to standard approaches used by health systems to invite patients to participate in health education programs. Caregiving During Crisis program, used for the control group, is a fully online, asynchronous, professionally designed continuing education course aimed at developing the competency of informal caregivers of community-dwelling persons living with dementia to ensure the safety of that person and themselves during this time of the COVID-19 pandemic. Caregivers might experience distress while completing self-administered questionnaires, which ask about their experiences as caregivers and their emotional health and well-being. During the Tele-Savvy online classes, it is possible that caregivers will experience sadness, anxiety, anger, and other emotions during the process of sharing the ADRD journey that their spouses, parents, or other relatives/care recipients have traveled, as well as their own caregiving responsibilities. They also might become fatigued during the online classes as well as during the times between classes when they are viewing educational videos or doing their homework. These are common stressors not outside of what they may ordinarily experience and they are free to stop participation in the programs at any time.

(ii) The research could not practicably be carried out without the requested waiver or alteration:

Inclusion of research informed consent would affect the scientific validity of studying a new process of implementing an efficacious intervention—the Tele-Savvy Program—for the underserved target population of family caregivers of older adults living with dementia in the two health systems participating in this pilot study. Offering the Tele-Savvy program as proposed in this pilot study is similar to standard approaches used by health systems to invite patients to participate in health education programs. One of the study sites, Emory, already offers the program as part of its standard practice.

(iii) The research involves using identifiable private information that could not practicably be carried out without using such information in an identifiable format:

Identifiable private information is required in order to contact caregivers and follow them over time. See section 11.3 below about how we will maintain participant confidentiality.

Additionally a HIPAA waiver will be requested for the purpose of collecting PHI as it relates to the practicability of contacting caregivers and tracking them in the correct medical records of patients. Caregiver PHI will be collected for the sole purpose of ensuring that caregiver data are stored in the correct EMR record, that of the patient for whom they are a caregiver.

(iv) The waiver or alteration will not adversely affect the rights and welfare of the subjects:

Caregivers will be provided with an information sheet that describes their participation in the research study and will have the option to Opt-in to participate or Opt-out. If they choose to participate or not, it will not adversely affect the rights and welfare of either their loved ones care or their own.

(v) Whenever appropriate, the subjects or legally authorized representatives will be provided with additional pertinent information after participation.

As part of this pragmatic trial, we will share results of the pilot study with relevant clinicians and clinical service administrators at both the UConn Health and Emory Healthcare systems. We also will provide a brief synopsis of study results written in lay language that the health care systems will be able to share with caregivers who participate in the study.

